1.3 Preliminary safety assessment results

Domestic Clinical Trials

The safety of Degarelix was investigated in a China Phase III active-controlled trial in Chinese patients (N = 283) receiving monthly Degarelix (subcutaneous injection) or Goserelin (subcutaneous injection) for 12 months. Adverse events reported in $\geq 5\%$ patients were showed in Table 1.

Table 1, Adverse Events occurred in >=5% Patients in the Groups by MedDRA System Organ Class and Preferred Term - Safety Analysis Set

	Degarelix 240/80mg	Goserelin 3.6mg
	(S.C.)	(S.C.)
	N=142	N=141
Any Adverse Event	76.1%	58.9%
General Disorder and administration site condition		
Injection site reactions	45.1%	1.4%
Injection Site Swelling	26.8%	0.7%
Injection Site Erythema	26.8%	
Injection Site Pain	24.6%	0.7%
Injection Site Mass	7.0%	
Pyrexia	12.7%	1.4%
Fatigue	5.6%	2.1%
Infections and Infestations		
Urinary tract infection	7.0%	7.8%
Vascular Disorders		
Hypertension	9.9%	10.6%

MedDRA version 18.0

Ferring Pharmaceuticals (Asia) Co., Ltd.

The most common adverse events in patients treated with Degarelix were injection site reactions, including injection swelling (26.8%), injection site erythema (26.8%), injection site pain (24.6%), and injection site mass (7.0%).

Most injection site reactions were mild or moderate in severity (2 patients with severe injection site reactions: 1 with severe injection erythema and 1 with severe injection site mass), and there is no hypersensitivity reaction of immediate onset. Adverse events mainly occurred in the initial stage of treatment, and their incidences were decreased with time. No patients discontinued from the trial due to injection site reactions.

Of abnormalities in hepatic function test, alanine aminotransferase (ALT) (with or without total bilirubin), aspartate aminotransferase (AST), and total bilirubin were comparable between the treatment groups. No patient developed increased ALT considered as serious adverse event, and no patient discontinued from the trial due to increased ALT.

ECG results showed that, there was no significant differences of mean change of QTcF between the treatment groups from baseline to Day 3 and to the end-of-trial visit.

QTcF >=500 msec occurred in 13 patients, including 7 (5%) patients in the Degarelix Group and 6 (4%) patients in the Goserelin Group.

Overall, the safety results from the trial were consistent with those of foreign pivotal studies, and were also consistent with the expected results in elderly patients of prostate cancer receiving androgen therapy; mo major safety problems were found.

Available data from clinical trials indicates that FIRMAGON® is generally well tolerated, with adverse events (AEs) generally being manageable and reversible with supportive care. The adverse event profile is similar to that of the GnRH agonists with the most frequently reported adverse drug reactions (ADRs) being related to the pharmacological activity of the product (testosterone inhibition). See detail information from China label of Degarelix .

Regulatory requirements

The China National Medical Products Administration (NMPA) on 11 Sep, 2018 formally approved the Marketing Authorization Application of imported FIRMAGON® in China. Due

Intensive Drug Monitoring Protocol Version: 1.0

Date: 11-May-2020

to the requirements on "Regulations for the Reporting and Monitoring of Adverse Drug Reactions" and the "Intensive Drug Monitoring Guidelines for Manufacturers", Marketing Authorization Holder (MAH) should report all adverse reactions and conduct intensive monitoring for new imported drugs within 5 years from the date of first approval.

Intensive Drug Monitoring (IDM) refers to drug safety monitoring activities carried out to further understand clinical use of drug, the occurrence of ADRs and its occurrence of characteristics or seriousness or incidence in real world practice. Based on the consideration, Ferring Pharmaceuticals (Asia) Co.,Ltd. (hereinafter referred to as "Ferring") plans to carry out IDM study and collect all patients' AEs whether or not related to the product use, with particular attention to the occurrence of important adverse reactions.

Ferring Pharmaceuticals (Asia) Co., Ltd.

2 Study Objective and Outcome measure

2.1 Objective

This safety research study focuses on the safety information used in the real world, based on known risks. The occurrence of adverse events of FIRMAGON® will be evaluated.

2.2 Outcome measure

• To evaluate safety and tolerability of degarelix one-month dosing regimen in Chinese patients diagnosed with prostate cancer and in need of Androgen Deprivation Therapy.

For the definition of SAEs/AEs, see section 6.

Ferring Pharmaceuticals (Asia) Co., Ltd.

3 Study Administrative Structure

In accordance with the "Regulations for the Reporting and Monitoring of Adverse Drug Reactions" and the "Intensive Drug Monitoring Guidelines for Manufacturers", the intensive monitoring for FIRMAGON® is initiated by Ferring, aimed to evaluate patient safety of using FIRMAGON® treatment in real-world practice. To this end, the Ferring has arranged members of related internal departments and delegated a Contract Research Organization (CRO) for monitoring drug safety. Before the study is implemented, it will be filed with the National Adverse Drug Reaction Monitoring Center.

3.1 Study Sites

This study is to select qualified hospitals which have signed contract with China Primary Healthcare Foundation as study sites. 138 target hospitals are in the charity support list. The charity will provide FIRMAGON® to patients who participate in this study. In order to ensure the representativeness of the sample, participating sites will cover all major regions across China, and China Primary Healthcare Foundation is recommended to enroll patients on a consecutive basis. The CRO will keep a record of the individuals responsible for each participating Study Site.

Ferring Pharmaceuticals (Asia) Co., Ltd.

4 Ethics

This study is an observational study where the existence of the study has no impact on the

patient except for collection of informed consent to use patients' data. Informed Consent

Form (ICF) will be reviewed and recorded by Central EC.

4.1 Ethical conduct of the Study

This study will be conducted in accordance with the protocol, the current version of the

Declaration of Helsinki, Good Pharmacoepidemiology Practices (GPP), ISPE GPP guideline

and any local regulations.

Ferring will ensure that the protocol, the patient Information Sheet/ICF and any amendments

are submitted to the Independent central Ethics Committees (IECs) according to local

requirements.

According to applicable regulations, we will:

• notify or obtain approval from the relevant IEC of the protocol, the patient Information

Sheet/ICF and any amendments

• submit required documents to the IEC, such as:

 \checkmark protocol deviation, safety information or summary of the study progress

according to the requirement (if applicable)

✓ notification of the end-of-study

✓ a summary of the study results

Ferring will keep an updated list of all submissions and approval dates of all documents

submitted to the IEC and will provide the Site Responsible with a copy of this list. Copies of

the documents will be distributed upon request.

4.2 Authorities

Ferring will send required documents to the regulatory authority and keep an updated list of

submission and approval dates and a copy of all documents submitted.

Page 14 of 35

Ferring Pharmaceuticals (Asia) Co., Ltd.

4.3 Patient Information and Written Informed Consent

This study is an observational study, even though patients will return to hospital and accept

monthly FIRMAGON® treatment, the staff of the charity must give the patient oral and

written information about the study in a form that the patient can understand and obtain the

patient's written consent before collection of identifiable patient information (hereinafter

referred to as personal data). Before consenting, the patient must be left with ample time to

consider and to pose questions. Since the study is observational, the consent only concerns

the data collection The decision to treat the patient is independent of the decision to enrol the

patient in the study.

The patient must agree that Ferring personnel, their representatives or IEC or regulatory

authority personnel may require direct access to the patient's data / personal records which

were collected, processed and stored in an anonymous form.

The patient must agree that his / her data will be processed and stored in an anonymous form

for evaluation of this study and any later overviews. Data may also be transferred in anonymous

form to third parties, e.g. other companies or authorities, that may be located in other countries

with potentially different regulations for data.

The patient will receive a copy of ICF after consenting.

The patient has the right to withdraw their consent at any time without prejudice. In the

Informed Consent Form it is stated that if consent is withdrawn, any data collected before

withdrawal of consent will be kept. The original Informed Consent Forms signed and dated by

the patient and investigators must be kept in the Charity.

For details, see the Informed Consent Form.

Page 15 of 35

Intensive Drug Monitoring Protocol Version: 1.0

Date: 11-May-2020

5 Study Design and Plan

This study is a multi-center, single-arm, non-interventional study among Chinese patients with prostate cancer needed androgen deprivation therapy receiving treatment with FIRMAGON®. 2500 patients who are prescribed FIRMAGON® according to clinical practice by doctors in hospitals will be enrolled in this study. This program will provide the minimum 6 doses and maximum 12 doses of FIRMAGON® to enrolled patients during one-year follow-up. Patients apply for enrollment in hospital, they will return to hospital every three months for medical assessment and other three doses of FIRMAGON® prescription during the study. 138 target hospitals are in the charity support list. The direct-to-patient pharmacy will distribute FIRMAGON to patients who are defined eligible by the doctor. The patient should bring the prescriptions and the last FIRMAGON® boxes to get other FIRMAGON®.

All enrollment patients will be followed up to collect safety information for one year from China Primary Healthcare Foundation from the 1st dose unless withdrawal of Informed Consent Form, dosing interrupted for 2 months or more than 2 months since last dose, lost to follow-up, death, or termination due to other reasons (defined in section 5.4), whichever comes first. Any AEs will be filled in Adverse Event Form (as Appendices), processing and submitting to relevant authorities.

5.1 Study Schedule

Planned Start of Study: Q1 2021

Planned the end of the last patient's follow-up Aug 2022

Planned completion of the Study Report: Dec 2022

The Ferring will ensure that End-of-Study notification is submitted to the concerned authorities and IEC for each site as locally required.

5.2 Discussion of Study Design

This IDM study is a non-interventional study to collect all AEs during the post-marketing drug use.

Ferring Pharmaceuticals (Asia) Co., Ltd.

AE data collection is the main purpose of the IDM programme. For all patients, the key

outcome measure is to evaluate the safety profile of FIRMAGON® in Chinese population in

real world clinical practice.

In reality, the willingness of hospitals to accept post-marketing trials is not high, and it is

difficult to enroll patients as well. Therefore, to fulfill regulatory requirements within timeline,

considering to combine the IDM with China Primary Healthcare Foundation. In this study, due

to enrollment of low-income patients with prostate cancer, the possibility of population

selection bias must be considered.

The sample size sets as 3000 patients or cover 80% of the patient exposure, meet either of these

two regulation requirements. Due to the low sales volume forecast, the sample size could be

decreased to 2500 patients per discussion with authority officer. The supportive documents will

be provided if there any other post-marketing surveillance study reports available. In any a

hospital participates in this program, most of its patients might have access to obtain

FIRMAGON® donations.

Although patients included in this study might not receive any direct benefit from the study,

the study will promote better understanding of the safety FIRMAGON® for prostate cancer

needed androgen deprivation therapy patients in a large, more generalizable population.

5.3 Selection of Study Population

5.3.1 Inclusion Criteria

Patient eligibility is determined according to the following criteria prior to entry into the

study:

1) Diagnosis as prostate cancer and need androgen deprivation therapy

2) Decision made to prescribe of FIRMAGON® prior to enrolment.

3) Willingness and ability to provide written informed consent.

4) The patients are from whom taken post-marketing drug FIRMAGON®.

5.3.2 Exclusion Criteria

Any patient who meets the following criterion will not be qualified for entry in this study:

Page 17 of 35

Ferring Pharmaceuticals (Asia) Co., Ltd.

- 1) Not signed Informed Consent.
- 2) Any patients who is unsuitable to participate in this study because of any other reasons will not be qualified to participate in this study.

5.4 Patient Discontinuation

The following events will result in patient discontinuation and should be recorded in the study database:

- 1) The doctors confirm that the patient does not meet the instructions of FIRMAGON® or is unsuitable for continued use;
- 2) The patient presents an intolerable adverse reaction;
- 3) Death;
- 4) The patient, his legal guardian or immediate family request the discontinuation of FIRMAGON® treatment;
- 5) The patient refuses to accept medical evaluation according to the procedure or protocol;
- 6) The patient automatically removes from the group after 2 months discontinuation of medication;
- 7) The patient sales, exchanges the donation drugs for profit purposes;
- 8) The application information provided by patients is confirmed as false information, including application form with patient's information, medical information (medical history, diagnoses, treatment, etc.) and follow up information, etc;;
- 9) The application is not within the time limit, or all the donation drugs have been distributed within cutoff day;
- 10) Suspension due to the policy adjustments or changes from regulatory authority.

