7.3 Data Management

The patients' data will be input into the charity's database by the delegated staff. The patients will be identified only by Study ID and patient number in the export database for analysis.

If the written informed consent of a patient is known not to be available in spite of it being required, data for this patient is not entered into or is deleted from the export database.

If a patient is included in the study in spite of being treated off-label (not according to the summary of product pharmacological study), data is kept in the database and analysed separately and as part of the overall analyses as described in the Statistical Analysis Plan.

The safety data (AEs report) filed in AE form will be input into global safety database. The current Standard Coding Instructions for coding of medical history, concomitant illness (MedDRA), concomitant medication (WHO-Drug) and adverse events/reactions (MedDRA) must be followed.

Ferring Pharmaceuticals (Asia) Co., Ltd.

8 Statistical Methods and Determination of Sample Size

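### Patients confirmed as off-label may leave adverse event follow-up early under 5.4(1), yet 7.3 analyses them as a group and 8.1 plans only crude percentages

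*Combined protocol and SAP*

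**What the plan says.** - **Entry (5.3.1, 5.3.2).** The disease criterion is "Diagnosis as prostate cancer and need androgen deprivation therapy" and the prescribing criterion is "Decision made to prescribe of FIRMAGON® prior to enrolment". Neither requires use within the label. The exclusions are missing consent and a general clause: "Any patients who is unsuitable to participate in this study because of any other reasons will not be qualified to participate in this study".
- **Discontinuation (5.4).** The list opens in mandatory terms: "The following events will result in patient discontinuation and should be recorded in the study database". Item 1 reads "The doctors confirm that the patient does not meet the instructions of FIRMAGON", followed by an alternative about unsuitability for continued use. Item 6 removes a patient after two months off medication.
- **End of follow-up (section 5).** Safety follow-up runs for one year from the first dose unless one of several events comes first. The list ends with "termination due to other reasons (defined in section 5.4), whichever comes first".
- **After follow-up (6.3).** Patients and health care providers may still report AEs spontaneously.
- **Off-label data (7.3).** The rule begins "If a patient is included in the study in spite of being treated off-label". It keeps the data and has them analysed separately and overall, with the details left to the statistical analysis plan (SAP).
- **Analysis (8.1 to 8.3).** Categorical data are given as frequencies and percentages on the full analysis set, without imputation. Fisher or chi-square tests between subgroups are possible. Person-time is not mentioned, and the documents do not describe the off-label analysis further.

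**The concern.** An off-label patient can enter, be discontinued once a doctor confirms the mismatch, and still belong to a group that 7.3 wants reported. Label status is a fact about the patient's use of the drug. Here it acts after entry as an event that ends observation, at a date set by when someone notices.

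Off-label use is part of the real-world use that intensive monitoring is meant to describe. If the confirmed off-label group is watched for less time and summarised by crude percentages, it will tend to show fewer AEs than the on-label group for that reason alone. That could be read as reassurance. The optional subgroup tests in 8.3 would carry the same distortion.

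**Working it through.** **Reading the rules together.** The plan gives no figure for this point, so there is none to reproduce.

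1. Nothing in 5.3 requires on-label use, and 7.3 expects that some off-label patients will be included.
2. If *instructions* in 5.4(1) means the label, a doctor's confirmation of mismatch is a discontinuation event.
3. Section 5 makes any 5.4 reason an end of the one-year safety follow-up. Active AE collection stops there, and only spontaneous reports (6.3) remain.
4. Section 7.3 then analyses these patients separately and overall, and 8.1 supplies percentages only.

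It follows that confirmed off-label patients have shortened observation, while unrecognised ones stay for the full year.

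**Illustration of direction and possible size.** The number of off-label patients and the timing of confirmation are not in the documents. Two assumptions are made: constant hazard, and a stop at month 3, the first scheduled reassessment. No section says that mismatch is found then.

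Formula: apparent proportion by month t = 1 − (1 − p)^(t/12), where p is the one-year risk.

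- Assumed p = 10%, t = 3: 1 − 0.90^0.25 = 2.6%.
- Hypertension, p = 9.9% (section 1.3, Table 1, degarelix arm): 2.6% at t = 3 and 5.1% at t = 6.
- Pyrexia, p = 12.7% (same table): 3.3% at t = 3 and 6.6% at t = 6.

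Section 1.3 reports that AEs in the earlier Chinese trial occurred mainly early in treatment. If all events of a given type fell within the first three months, a stop at month 3 would lose none of them and 10% would stay 10%. For events with a falling hazard, the apparent figure therefore lies between 2.6% and 10%. Injection site reactions (45.1% in Table 1) probably sit towards the upper, little-loss end of the corresponding range. The constant-hazard figures suit later-onset events better.

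**Effect on the overall incidence.** Assume a share s of patients is truncated at month 3 and p = 10%. The overall figure is (1 − s) × 10% + s × 2.6%.

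- s = 1%: 9.9%.
- s = 5%: 9.6%.

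**What person-time does.** Under constant hazard, the rate is −ln(1 − 0.10) = 0.105 per patient-year whether observation lasts 3 or 12 months, so a person-time rate removes this distortion. If the hazard falls over time, a rate from the first three months exceeds the 12-month rate. Person-time reporting therefore helps but does not replace the missing observation.

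**The case against.** **Not a contradiction.** A reader might infer that 5.4 and 7.3 contradict each other. They do not. Section 7.3 is worded as a contingency about keeping and analysing data, which is compatible with ending participation. This objection stands.

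**The meaning of 5.4(1) is an interpretation.** The label is not in the documents, and the clause goes on to mention unsuitability for continued use, so it can be read as a doctor's judgement about continuing. The general exclusion for unsuitability, and distribution only to patients whom the doctor finds eligible, may also keep some off-label patients out. This stands as a caution. Reading *instructions* as the label is still natural, and 7.3 shows that such patients are expected.

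**The size is unknown.** Month 3 and constant hazard are assumptions, and the second fits poorly with the mainly early AEs reported in section 1.3. A reader might take 2.6% as a forecast, or infer that the main safety percentages are materially biased. The documents support neither.

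**Mitigations exist.** Spontaneous reports remain possible. Section 5.6 collects treatment duration and AE onset dates, so exposure-adjusted reporting is feasible, and the SAP is still to be finalised. This stands in part. Spontaneous reporting does not equal active collection, and no analysis can recover AEs that were never collected.

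**The issue is wider.** Section 5 ends follow-up for every 5.4 reason, including intolerable adverse reactions. That is true. The off-label case is still distinct because 7.3 calls for a separate analysis of exactly these patients.

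**Conclusion.** The point holds as a matter of unreconciled rules. If *instructions* means the label, doctor-confirmed off-label patients have follow-up that ends when the mismatch is noticed, and the crude percentages in 8.1 would understate their AE incidence relative to on-label patients. A reader might infer that all off-label patients are truncated, but 5.4(1) acts only on confirmed cases.

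The size cannot be computed from the documents. The fall from 10% to about 2.6% is an illustration that rests on constant hazard and an assumed stop at month 3, and the loss is smaller for early events. The effect on overall incidence is probably negligible: 9.9% to 9.6% instead of 10% if 1% to 5% of patients were affected, a range that is itself assumed. The weakness lies in the separate off-label analysis. A modest change of wording and data collection is worth making.

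**What to change.** 1. Reconcile sections 5, 5.3, 5.4 and 7.3. State whether *instructions* in 5.4(1) means the label. State that an off-label finding does not by itself end AE observation, which would run to one year from the first dose unless consent is withdrawn or the patient dies or is lost to follow-up.
2. Reconcile the two-month interruption rule (section 5 and 5.4 item 6) with this for these patients. Otherwise it could end their observation by another route.
3. Add on-label or off-label status, with the reason, to the baseline data in 5.6.
4. In the SAP, report the 7.3 off-label analysis with person-time (exposure-adjusted) rates alongside percentages, using the treatment duration and AE onset dates already collected.

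No position is taken on drug supply or on whether treatment continues.

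The cost is some wording, one data field and a few AE contacts by the charity. Those contacts are not entirely free: the three-monthly returns are tied to assessment and the next prescription, so they may have stopped by then. The study summary also says that no data or monitoring beyond current practice will be added, so that statement should be checked against the new wording.
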